6.2 Subject Exclusion Criteria

- Pregnant or lactating women
- No acute intercurrent disease including active potentially life-threatening infection or heart disease, with New York Heart Association Class II or greater, or clinical evidence of congestive heart failure.
- History of hypersensitivity reactions attributed to a conventional formulation of doxorubicin HCL or components of Doxil
- No demonstrated resistance to prior treatment with Targretin®.
- Patients using class 1 high potency topical therapy will not be allowed on to the study.

Please note copies of source documentation confirming eligibility for patients enrolling at outside institutions must be provided to the MSKCC CTO registrar at the time of registration. Please fax to [contact].

7.0 RECRUITMENT PLAN

The trial will require 37 patients to meet study endpoints. With the targeted annual accrual of 10-15 patients, this study will require about 3 years to complete accrual.

Potential research subjects will be identified by a member of the patient's treatment team, the protocol investigator, or research team at Memorial Sloan-Kettering Cancer Center (MSKCC-Lead Center), M. D. Anderson Cancer Center, New York University Medical Center, Hackensack University Medical Center, and Roswell Park Cancer Institute. If the investigator is a member of the treatment team, s/he will screen their patient's medical records for suitable research study participants and discuss the study and their potential for enrolling in the research study. Potential subjects contacted by their treating physician will be referred to the investigator/research staff of the study.

Consent Process

Participation is voluntary. The patient must be aware of the nature of his/her disease and willingly consent after being informed of the procedures to be followed, the experimental nature of the therapy, alternatives, potential benefits, side effects, risks and discomforts. All patients will be required to sign a statement of informed consent that conforms to IRB guidelines. Informed consent will be documented by the use of a written consent form that has been approved by the institution's IRB. Three copies of the informed consent will be signed and dated by the patient or the patient's legally authorized representative. One copy will be given to the patient, one copy will be filed in the patient's medical record, and one copy will be retained in the Protocol Participant Registration (PPR) Office. Written consent will be obtained by either the principal investigators or participating investigators.

Memorial Sloan-Kettering Cancer Center
IRB Protocol

IRB#: 05-098 A(6)

8.0 PRETREATMENT EVALUATION

- History and physical examination. Karnofsky Performance Status. A dermatologist will make skin score determination. A two item self-reported pruritus questionnaire will be administered. (to be done within 14 days prior to entry into the study)
- Laboratory Evaluations:
 - f* CBC, platelet count, differential count with absolute neutrophil count (to be done within 14 days prior to entry into the study)
 - f* Serum chemistry panel: electrolytes, BUN, creatinine, SGOT (AST), SGPT (ALT), alkaline phosphatase, LDH, total bilirubin, albumin, total protein, calcium, amylase, uric acid. After at least an eight-hour fast: glucose, cholesterol, triglycerides (to be done within 14 days prior to entry into the study)
 - f* T4, TSH (to be done within 14 days prior to entry into the study)
 - f* Patients must have a MUGA scan or 2-d echocardiogram indicating an ejection fraction of $\geq 50\%$ within 42 days prior to first dose of study drug. The method used at baseline must be used for later monitoring.
- Urinalysis (to be done within 7 days prior to entry into the study)
- Patients with stage IV disease (TNM): CT of chest, abdomen and pelvis (to be done within 6 weeks prior to entry into the study)
- For women of child bearing potential: beta-HCG pregnancy test (to be done within 7 days prior to entry into the study)
- Patients with Sézary syndrome will have a Sézary cell count and/or flow cytometry panel (to be done within 14 days prior to entry into the study)

9.0 TREATMENT/INTERVENTION PLAN

Dosing/Regimen:

Doxil@Dose: 20mg/m² intravenously. Frequency: 2 weeks. Number of Cycles: 8 (16 weeks)

To minimize the risk of infusion-related reactions, the first infusion of DOXIL should be administered over 90 minutes as follows:

10 mL over 1st 10 minutes

**Memorial Sloan-Kettering Cancer Center
IRB Protocol**

IRB#: 05-098 A(6)

20mL over next 10 minutes
 40mL over next 10 minutes
 then, complete the infusion over a total of 90 minutes

Targretin® Dose: 300mg/m² orally Frequency: Daily for at least 16 weeks to be started within 2 weeks of tumor assessment (It is recommended that patients be treated prophylactically with an agent to lower triglycerides such as fenofibrate or atorvastatin)

Schema:

Doxil® every 2 weeks x 8 → response assessment → within 2 weeks of tumor assessment:
 Targretin® x 16 weeks → response assessment, CR/PR → continue Targretin® until relapse.

Dose Modification Guidelines

Patients should be carefully monitored for toxicity. Adverse events, such as palmar-plantar erythrodyesthesia (hand-foot syndrome), hematologic toxicities, and stomatitis may be managed by dose delays and adjustments. Following the first appearance of Grade 1 toxicity, patients will be prescribed topical betamethasone dipropionate (Diprolene) 0.05% gel to use twice daily on hands and feet only until signs and symptoms resolve. Following the first appearance of a Grade 2 or higher adverse event, the dosing should be adjusted or delayed as described in the following tables. Once the dose has been reduced, it should not be increased at a later time.

PALMAR – PLANTAR ERYTHRODYESTHESIA	
Toxicity Grade	Dose Adjustment
1 (mild erythema, swelling, or desquamation not interfering with daily activities)	Redose unless patient has experienced previous Grade 3 or 4 toxicity. If so, delay up to 2 weeks and decrease dose by 25%. Return to original dose interval.
2 (erythema, desquamation, or swelling interfering with, but not precluding normal physical activities; small blisters or ulcerations less than 2 cm in diameter.)	Delay dosing up to 2 weeks or until resolved to Grade 0-1. If after 2 weeks there is no resolution, Doxil® should be discontinued.

**Memorial Sloan-Kettering Cancer Center
IRB Protocol**

IRB#: 05-098 A(6)

3 (blistering, ulceration, or swelling interfering with walking or normal daily activities; cannot wear regular clothing)	Delay dosing up to 2 weeks or until resolved to Grade 0-1. Decrease dose by 25% and return to original dose interval. If after 2 weeks there is no resolution, Doxil® should be discontinued.
4 (diffuse or local process causing infectious complications, or a bed ridden state or hospitalization)	Delay dosing up to 2 weeks or until resolved to Grade 0-1. Decrease dose by 25% and return to original dose interval. If after 2 weeks there is no resolution, Doxil® should be discontinued.

HEMATOLOGICAL TOXICITY			
GRADE	ANC	PLATELETS	MODIFICATION
1	1500 – 1900	75,000 - 150,000	Resume treatment with no dose reduction
2	1000 - <1500	50,000 - <75,000	Wait until ANC > 1,500 and platelets > 75,000; redose with no dose reduction
3	500 – 999	25,000 - <50,000	Wait until ANC > 1,500 and platelets > 75,000; redose with no dose reduction
4	<500	<25,000	Wait until ANC > 1,500 and platelets > 75,000; redose at 25% dose reduction or continue full dose with cytokine support.

STOMATITIS	
Toxicity Grade	Dose Adjustment
1 (painless ulcers, erythema, or mild soreness)	Redose unless patient has experienced previous Grade 3 or 4 toxicity. If so, delay up to 2 weeks and decrease dose by 25%. Return to original dose interval.
2 (painful erythema, edema, or ulcers, but can eat)	Delay dosing up to 2 weeks or until resolved to Grade 0-1. If after 2 weeks there is no resolution, Doxil® should be discontinued.

**Memorial Sloan-Kettering Cancer Center
IRB Protocol**

IRB#: 05-098 A(6)

3 (painful erythema, edema, or ulcers, and cannot eat)	Delay dosing up to 2 weeks or until resolved to Grade 0-1. Decrease dose by 25% and return to original dose interval. If after 2 weeks there is no resolution, Doxil® should be discontinued.
4 (requires parenteral or enteral support)	Delay dosing up to 2 weeks or until resolved to Grade 0-1. Decrease dose by 25% and return to original dose interval. If after 2 weeks there is no resolution, Doxil® should be discontinued.

Myeloid and erythroid growth factor support will be permitted according to institutional or National Comprehensive Cancer Network (NCCN) guidelines.

In the event of Targretin® dose-limiting toxicity (NCI toxicity grade 3 or 4 or serum triglycerides ≥ 800 mg/dL), the 300 mg/m²/day dose may be reduced to 200 mg/m²/day, or a 200 mg/m²/day dose may be reduced to 100 mg/m²/day. Suspension of Targretin capsules treatment may accompany dose reductions for up to 14 days, if necessary for recovery from toxicity. Patients with dose-limiting toxicities at the 100 mg/m²/day dose level should be withdrawn from the study.

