4.2 Intervention

Patients will be treated with intravenous Doxil® every two weeks for 8 doses (16 weeks). Responses will be assessed. They will then receive Targretin® orally for at least 16 weeks. Patients who achieve a CR or PR may continue on Targretin® until relapse.

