5.0 THERAPEUTIC/DIAGNOSTIC AGENTS

Doxil® (doxorubicin HCl liposome injection)

Doxil® (doxorubicin HCl liposome injection) is doxorubicin hydrochloride (HCl) encapsulated in STEALTH® liposomes for intravenous administration. The active ingredient of Doxil® is doxorubicin HCl, a cytotoxic anthracycline antibiotic isolated from *Streptomyces peucetius* var. *caesius*. The mechanism of action of doxorubicin HCl is thought to be related to its ability to bind DNA and inhibit nucleic acid synthesis. Cell structure studies have demonstrated rapid cell penetration and perinuclear chromatin binding, rapid inhibition of mitotic activity and nucleic acid synthesis, and induction of mutagenesis and chromosomal aberrations.

If at anytime the patient develops progressive disease he/she will be taken off study and referred for alternative therapy.

**Memorial Sloan-Kettering Cancer Center
IRB Protocol**

IRB#: 05-098 A(6)

If at anytime the patient develops unacceptable toxicity he/she will be removed from study.

If at anytime the patient is found to be ineligible for the protocol as designated in the section on Criteria for Patient/Subject Eligibility (i.e., a change in diagnosis), the patient will be removed from the study.

Doxil[®] is doxorubicin HCl encapsulated in long-circulating STEALTH[®] liposomes. Liposomes are microscopic vesicles composed of a phospholipid bilayer that are capable of encapsulating active drugs. The STEALTH[®] liposomes of Doxil[®] are formulated with surface-bound methoxypolyethylene glycol (MPEG), a process often referred to as pegylation, to protect liposomes from detection by the mononuclear phagocyte system (MPS) and to increase blood circulation time.

Doxil[®] (doxorubicin HCl liposome injection) is indicated for:

DOXIL[®] (doxorubicin HCl liposome injection) is indicated for the treatment of patients with ovarian cancer whose disease has progressed or recurred after platinum-based chemotherapy.

DOXIL[®] (doxorubicin HCl liposome injection) is also indicated for the treatment of AIDS-related Kaposi's sarcoma in patients with disease that has progressed on prior combination chemotherapy or in patients who are intolerant to such therapy.

These indications are based on objective tumor response rates. No results are available from controlled trials that demonstrate a clinical benefit resulting from this treatment, such as improvement in disease-related symptoms or increased survival.

Doxil Study Drug Supplier/Accountability

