10.0 EVALUATION DURING TREATMENT/INTERVENTION

10.1 Treatment visits every 2 weeks for Doxil® administration for 16 weeks. At each visit: history, physical exam, KPS, toxicity assessment, CBC, platelet count.

10.2 Tumor assessment within 2 weeks following the last dose of Doxil®, optimally between 7 and 14 days. For patients with stage IV disease (TNM) with baseline lymphadenopathy on CT scans of chest, abdomen and pelvis: repeat CT scans of chest, abdomen and pelvis. Patients with Sezary syndrome will have Sézary cell count and/or flow cytometry. Patients who have a CCR should have a biopsy to document a pathological CR. Two item self-reported pruritus questionnaire will be administered at time of tumor assessment. The details for tumor assessments at 16 and 32 weeks are described in Section 12.0 and in the Table in Appendix 3.

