10.3 Cardiac Safety Monitoring

All patients will be monitored for a decrease in LVEF based on the criteria below: Baseline Left Ventricular Ejection Fraction (LVEF) determinations will be performed on all patients prior to enrollment in the trial. Patients will not be enrolled if LVEF <50%. If during treatment the LVEF falls to $\leq 45\%$, or the ejection fraction (LVEF) falls by 20% from the baseline level, Doxil® will be discontinued. The investigator

**Memorial Sloan-Kettering Cancer Center
IRB Protocol**

IRB#: 05-098 A(6)

may verify the LVEF from a MUGA by obtaining an ECHO with cardiac consultation. If there is no evidence of cardiac damage determined by ECHO the patient may continue on treatment.

MUGA or ECHO (LVEF) Schedule for all patients:

- f* Cumulative anthracycline dose of $< 350\text{mg}/\text{m}^2$: physicians discretion
- f* Cumulative anthracycline dose of $\geq 350\text{mg}/\text{m}^2$: every two cycles

10.4 Within 2 weeks of tumor assessment: history, physical exam, KPS, CBC, platelet count, total bilirubin, SGOT (AST), SGPT (ALT), creatinine, uric acid, fasting triglycerides and cholesterol, T4, TSH.

10.5 Within 2 weeks after tumor assessment begin oral Targretin® for 16 weeks.

10.6 Followup visits: at 2 weeks, 4 weeks, 8 weeks, 12 weeks, 16 weeks: history, physical examination, KPS, CBC, platelet count, total bilirubin, SGOT (AST), SGPT (ALT), creatinine, uric acid, fasting triglycerides and cholesterol, T4, TSH. Tumor assessment at 16 weeks on Targretin® including self-reported pruritus questionnaire. Imaging with CT scans of the chest, abdomen and pelvis will be repeated at 16 weeks for stage IV patients if initial lymphadenopathy was present. Patients with Sézary syndrome will also have Sézary cell counts and/or flow cytometry repeated at 16 weeks. Responding patients may continue on Targretin® until progression. Followup visits will be at least every 3 months for 5 years or until signs or symptoms of tumor progression.

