Responses will be determined by the criteria described in the table below. Progression of disease while on treatment should be confirmed by a second assessment 1-4 weeks later so that patients who experience a temporary flare of disease due to skin infection or other intercurrent illnesses are not removed from the study prematurely.

Assessment	Description	Status
Completely clear	No evidence of disease; 100% improvement	CCR
Marked Improvement	Greater than or equal to 50% decrease in skin scores compared to baseline and improvement is maintained for 4 weeks	PR
Slight Improvement	Less than 50% decrease in skin scores compared to baseline	SD
Worse	$\geq 25\%$ increase in skin scores compared to baseline while the patient is actively taking the study drug or $\geq 50\%$ increase in the sum of the products of the greatest diameters of pathologically positive lymph nodes (should be documented by biopsy) compared to baseline while the patient is actively taking the study drug.	PD

Assessment of Overall Skin Disease

Pruritus Relief (Appendix 1)

The intensity of pruritus will be evaluated by the patient at baseline, at the week 16 (end of treatment with Doxil®) and week 32 (after 16 weeks of treatment with Targretin®) using a 1-10 point scale, where 0 is no pruritus and 10 is the worst imaginable pruritus. A 3-point decrease in pruritus intensity confirmed by a second assessment at least 4 weeks later without an increase in the use of anti-pruritic medications is considered clinically significant in those whose pruritus score is ≥ 3 on the 0-10 point scale at baseline.

4. As a secondary goal, index lesion severity will be evaluated by a modified Composite Assessment Scale (Appendix 2). These are measurements of skin disease that have been employed and validated in the phase II-III studies of Targretin® and in the current MSKCC trial of Targretin® of Intron-A® (IRB #01-128) in CTCL. Up to 4 index skin lesions will be chosen from representative patch, plaque and tumor lesions, and erythrodermic lesions. For erythrodermic patients, a 10x10 cm. area, easily identified by anatomic landmarks will be chosen and assessed by the same scale. These index lesions will be photographed and assessed at the same time as the SWAT assessment.

In the Phase II-III studies of Targretin capsules in CTCL, the Composite Assessment (CA) of Index Lesion Disease Severity was based on a core element of the summation of index lesion

**Memorial Sloan-Kettering Cancer Center
IRB Protocol**

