14.0 BIOSTATISTICS

This is a phase II, multi-center, open-label, single arm trial. The goal of this trial is to improve response rate and prolong progression-free survival in patients with cutaneous T-cell lymphomas with the sequential use of Targretin® after an optimal course of Doxil®. The primary endpoint is progression-free survival at 12 months. Based on historical data, the median progression-free is 12 months for treatment of CTCL with Doxil®. With the new treatment, this trial will be considered as promising if the probability of progression-free at 12 months is 70%. Thirty seven patients are needed in this trial with conventional type I error 0.05 and power 0.8. This trial would be considered to be promising for further study if 24 or more patients are progression free at one year. There is 80% chance of observing 24 or more progression-free out of 37 patients if the true rate is 70% or better.

**Memorial Sloan-Kettering Cancer Center
IRB Protocol**

IRB#: 05-098 A(6)

The second endpoints are complete response and partial response rates.

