16.0 DATA MANAGEMENT ISSUES

A Research Study Assistant (RSA) will be assigned to the study. The responsibilities of the RSA include project compliance, data collection, abstraction and entry, data reporting, regulatory monitoring, problem resolution and prioritization, and coordinate the activities of the protocol study team.

The data collected for this study will be entered into a secured database (Clinical Research Database, CRDB) at Memorial Sloan-Kettering Cancer Center.

Standardized Case Report Forms (CRFs) have been generated for this study. Affiliate sites will be responsible for filling out these MSKCC case report forms. Blank case report forms will be sent to the data managers at each site (for photocopying and use). These forms and the

Memorial Sloan-Kettering Cancer Center IRB Protocol

IRB#: 05-098 A(6)

required source documentation must be submitted to MSKCC in a timely fashion (please see Appendix 4 for schedule of data collection forms). When a patient goes off-study all CRFs are required to be sent to MSKCC no later than 4 weeks after the off-study date. Participating sites must fax case report forms bimonthly to: [contact] to the attention of the RSA. Forms can also be mailed to the address below.

Memorial Sloan-Kettering Cancer Center
Clinical Trials Office
[name]
[name]
[name]

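### Progression is defined only while on study drug, and toxicity takes patients off the study, so the 12-month status of off-drug patients may be miscounted or lost

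*Combined protocol and SAP*

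**What the plan says.** **Endpoint and rule.** Section 14 makes progression-free survival at 12 months the primary endpoint and calls the regimen promising if 24 or more patients are progression-free at one year. It adds: "There is 80% chance of observing 24 or more progression-free out of 37 patients if the true rate is 70% or better". It gives no rule for a patient whose status is unknown or who worsens off drug.

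**Definition of progression.** The response table in Section 12.7 defines skin progression as a rise of at least 25%: "increase in skin scores compared to baseline while the patient is actively taking the study drug". The nodal limb (a rise of at least 50%) carries the same on-drug condition. No other measured criterion is given.

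**Who stays on drug.** Section 4.2 says "Patients who achieve a CR or PR may continue on Targretin® until relapse". It does not say what happens to stable-disease patients after 16 weeks of Targretin.

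**Toxicity.** For Targretin, Section 9 says "Patients with dose-limiting toxicities at the 100 mg/m²/day dose level should be withdrawn from the study". Sections 5 and 13 both say "If at anytime the patient develops unacceptable toxicity he/she will be removed from study". By contrast, the Doxil rules for hand-foot syndrome and stomatitis (Section 9) and for LVEF (Section 10.3) stop Doxil only.

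**Follow-up and assessment.** Section 10.6 says "Followup visits will be at least every 3 months for 5 years or until signs or symptoms of tumor progression". On tumor assessment, Section 10.2 says "The details for tumor assessments at 16 and 32 weeks are described in Section 12.0 and in the Table in Appendix 3". Appendix 3 ends at weeks 30 to 32. Section 16 says "When a patient goes off-study all CRFs are required to be sent to MSKCC no later than 4 weeks after the off-study date".

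**The concern.** There are two mechanisms, and they act in opposite directions.

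- **Off-drug worsening.** A patient who stops drug without progression and then worsens before month 12 does not meet the written definition. Taken literally, that patient counts as progression-free. This raises the count and makes it easier for an inactive regimen to reach 24.
- **Lost status.** A patient removed from the study for toxicity before progressing may have no status at 12 months. Section 14 speaks of observing progression-free patients out of 37, so the natural reading is that an unknown is not a success. This lowers power.

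The decision is a fixed count with almost no slack, so one or two patients matter. No skin score is scheduled near month 12 that would settle either case.

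**Working it through.** **Inputs from Section 14.** N = 37; cutoff 24; historical median 12 months, so the null 12-month rate is p0 = 0.50; target rate p1 = 0.70. Whether the type I error is one- or two-sided is not stated; one-sided reproduces the plan.

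**The plan's own figures**, exact binomial:

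- P(X ≥ 24 | 37, 0.50) = 0.0494
- P(X ≥ 24 | 37, 0.70) = 0.8071

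Both match the stated 0.05 and 0.80.

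**Off-drug worsening.** Assumptions, none of them from the documents:

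- PFS is exponential with median 52 weeks, and month 12 is week 52 from first dose.
- A share q of patients still progression-free at week 32 is off drug from then on.
- Off-drug patients have the same hazard as the others.

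Steps:

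- S(32) = 0.5^(32/52) = 0.6528.
- Chance of progressing between weeks 32 and 52, given none before: 1 − 0.5/0.6528 = 0.234.
- If a fraction u of off-drug progressions goes uncounted, the counted progression-free rate under the null is 0.5 + q × u × (0.6528 − 0.5).
- Off-drug patients = 37 × 0.6528 × q. Uncounted progressions = 37 × 0.1528 × q × u.
- Type I error = P(X ≥ 24 | 37, counted rate).

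| q | Patients off drug | Uncounted (u = 1) | Rate (u = 1) | Type I error (u = 1) | Rate (u = 0.5) | Type I error (u = 0.5) |
|---|---|---|---|---|---|---|
| 0.1 | 2.4 | 0.57 | 0.5153 | 0.0715 | 0.5076 | 0.0597 |
| 0.2 | 4.8 | 1.13 | 0.5306 | 0.1005 | 0.5153 | 0.0715 |
| 0.3 | 7.2 | 1.70 | 0.5458 | 0.1373 | 0.5229 | 0.0851 |

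**Lost status.** If k patients have unknown status and count as non-successes, 24 successes must come from the other 37 − k. Power is P(X ≥ 24 | 37 − k, 0.70) and type I error is P(X ≥ 24 | 37 − k, 0.50). The range k = 1 to 3 is assumed.

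| k | Power | Type I error |
|---|---|---|
| 0 | 0.807 | 0.049 |
| 1 | 0.737 | 0.033 |
| 2 | 0.652 | 0.020 |
| 3 | 0.554 | 0.012 |

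**The case against.** **The on-drug clause may only be loose wording.** Section 12.7 asks for confirmation of progression that occurs during treatment, which implies that progression can also occur after it. Section 10.6 follows patients until signs or symptoms of progression with no on-drug condition, and Section 14 does not cite the Section 12 clause. A clinician who saw clear worsening off drug would probably not report the patient as progression-free. This stands as a reason to expect that only part of the off-drug progression would go uncounted, hence the columns with half recognised. It does not supply an off-drug criterion. The endpoint would then rest on individual judgment in an open-label, single-arm, multi-center trial.

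**Follow-up may already cover everyone.** Section 10.6 names progression as the only early stop to visits. Section 16 sets a deadline for forms and does not forbid follow-up, and the Patient Status & Outcome Form in Appendix 4 is due when applicable, not at the off-study date. Section 12.7 also speaks of removal from study where stopping treatment seems to be meant. All this makes lost status less likely. Still, Section 10.6 does not say that it covers patients removed for toxicity, and the protocol uses drug-only wording elsewhere, so a site could fairly take removal literally.

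**The numbers of affected patients are assumed.** That is true. Lost status may be rare, because two Targretin dose reductions come before withdrawal and triglyceride-lowering prophylaxis is recommended.

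**Stronger readings that the documents do not support:**

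- A reader might infer that every toxicity stop ends study participation. The specific Doxil rules named above stop only the drug.
- A reader might infer that patients with unknown status would be counted as successes. The wording of Section 14 does not favour that.
- A reader might infer that stable-disease patients must stop Targretin after 16 weeks. Section 9 gives at least 16 weeks and does not forbid longer treatment.

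**Conclusion.** The point holds as a gap in the endpoint rules and should be fixed. As written, the only progression definition cannot be applied to off-drug patients, and the toxicity rules leave it unclear whether removed patients are still followed to month 12.

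It is not an error in sample size: N = 37, the cutoff of 24, type I error 0.049 and power 0.807 are right when every status is known. Nor do the documents show that the type I error is in fact inflated. Under assumed off-drug shares of 10 to 30% from week 32, it would be about 0.072 to 0.137 if no off-drug progression is counted and 0.060 to 0.085 if half are. One to three unknown statuses would leave power at 0.737, 0.652 or 0.554. At zero affected patients nothing changes. The two effects should not be relied on to cancel, since they concern different patients at unknown rates. Confidence is medium, because the size rests on these assumptions and on how literally sites read the text.

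**What to change.** 1. **Section 12.7:** delete the on-drug condition from both the skin and the nodal limb of the progression definition.
2. **Sections 5, 9 and 13:** state that toxicity takes the patient off study drug, and that the patient stays on study for follow-up under Section 10.6.
3. **Section 10.6 and Appendix 3:** at the existing 3-monthly visit nearest month 12, record a skin score for every patient without progression, on or off drug.
4. **Section 14:** keep all treated patients in the 37, count an unknown 12-month status as not progression-free, and report how many are unknown.

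**Cost.** A wording amendment, a few extra visits for off-drug patients, and one skin score at a visit already planned. The count becomes slightly conservative: one unknown gives type I error 0.033 and power 0.737, so steps 2 and 3 matter for keeping unknowns rare. N and the cutoff do not change.

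How to count patients who start another CTCL therapy is a separate choice of estimand, and a month-12 CT would be an added procedure. Neither is needed for this correction.
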